The Effect of Nursing Counseling Perceived Stress, Coping and Birth Outcomes Among Pregnant Women

Study Protocol

Before commencing the study, approval from the ethics committee was obtained, from the Ondokuz Mayıs University Medical Practices Ethics Committee (see Appendix 1), and research permission was granted by OMUSUVAM (see Appendix 2). Pregnant women at risk of preterm birth were enrolled in the study after obtaining both written and verbal consent from them (see Appendix 3-4). It was emphasized that they were free to withdraw from the research at any time of their choosing.

Statistical Analysis Plan

Data analyses were performed via the SAS (Statistical Analysis System Institute, Cary, North Caroline) 9.4 Program. Scale data, including mean and standard deviations, were computed for both the experimental and control groups. Here, a focus was given to the dependent variables considered. A t-test was performed to examine the significance of the differences between the two groups in terms of the dependent variables held. A comparison of the pre-test, interim follow-up and post-test measurements for the participants in both the experimental and control groups, as based on the dimension of time, was carried out using repeated measures analysis of variance. Mean and standard deviation from descriptive statistics were used for the variables of the study determined by measurement, and number and percentage were used for the variables determined by counting. In pairwise comparisons between variables with two categories, t-test between independent groups was applied, and Analysis of Variance (F test) was applied to find differences between variables with three or more categories. In evaluating the pre-test, interim follow-up and post-test findings of the experimental and control groups; To compare the measurements taken from the same pregnant women at different follow-ups, interdependent groups or paired observation t-test was used, and Chi-Square analysis was used to reveal the relationship between the variables answered as open-ended questions in the findings determined by the measurement. One-way Repeated Measurement Variance Analysis was used in the analysis of more than one variable taken from the same pregnant women. Cronbach Alpha coefficient was used to calculate the reliability coefficients of the scale and its sub-dimensions. The value of 0.05 was accepted as the significance level throughout the study.

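### The group comparison of the repeated scale scores makes no stated use of the pre-test score as a covariate, although that score is collected

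*Combined protocol and SAP*

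**What the plan says.** The Statistical Analysis Plan (unnumbered, in the combined protocol and SAP) describes three measurement times in both groups: "A comparison of the pre-test, interim follow-up and post-test measurements for the participants in both the experimental and control groups". These are compared "as based on the dimension of time, was carried out using repeated measures analysis of variance".

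The test of the group difference is given as: "A t-test was performed to examine the significance of the differences between the two groups in terms of the dependent variables held". A further sentence repeats the same kind of test: "In pairwise comparisons between variables with two categories, t-test between independent groups was applied". Neither names a covariate, a time point or a change score.

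The other methods stated are:
- an F test: "Analysis of Variance (F test) was applied to find differences between variables with three or more categories";
- a paired test: "To compare the measurements taken from the same pregnant women at different follow-ups, interdependent groups or paired observation t-test was used";
- a second mention of repeated measures: "One-way Repeated Measurement Variance Analysis was used in the analysis of more than one variable taken from the same pregnant women";
- chi-square for categorical answers and Cronbach's alpha for reliability.

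The significance level is 0.05, with sidedness not stated. The SAP does not name the scales; from the study title they are taken to be perceived stress and coping. The available text gives no sample size, SD, power target, pre/post correlation or allocation method.

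**The concern.** Each woman's pre-test score on a scale is usually one of the best predictors of her later score on that scale. A group comparison that leaves it out keeps predictable between-woman variation in the error term. A change-score comparison uses the pre-test, but with a fixed coefficient of 1, which over-corrects when the correlation is moderate.

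If women were randomised, this costs precision: wider intervals and lower power for the counseling effect. The validity of each single test is not in question, and nothing here concerns multiple testing.

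If women were not randomised, more is at stake. Post-score, change-score and ANCOVA estimates then rest on different assumptions about how a baseline difference would have evolved without counseling. They can disagree, and the present text does not show which was used.

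**Working it through.** **Reading the text.** Taking each stated method in turn:
- The independent-groups t-test compares the groups, unadjusted as described.
- The F test is for three or more categories, so it is not the two-group comparison.
- The paired t-test is within women.
- The repeated measures ANOVA mentions both groups, but names only time and no group or interaction term. A later sentence calls a repeated measures analysis one-way.
- Chi-square and Cronbach's alpha do not estimate a difference in scale scores.

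No ANCOVA or baseline covariate appears. If the ANOVA was meant as group by time, its pre/post contrast is a change-score comparison, so both readings are covered below.

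**Inputs.** There is no documented figure to reproduce. Assumptions: equal SDs set to 1, equal groups, pre/post correlation ρ = 0.3, 0.5, 0.7, and 30 women per group (N = 60).

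**Large-sample relative variance of the group difference.** Post score: 1. Change score: 2(1 − ρ). ANCOVA: 1 − ρ². Hence ANCOVA/change = (1 − ρ²) / [2(1 − ρ)] = (1 + ρ)/2.

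| | ρ = 0.3 | ρ = 0.5 | ρ = 0.7 |
|---|---|---|---|
| Post score | 1.00 | 1.00 | 1.00 |
| Change score | 1.40 | 1.00 | 0.60 |
| ANCOVA | 0.91 | 0.75 | 0.51 |
| Saving vs post score | 9% | 25% | 49% |
| Saving vs change score | 35% | 25% | 15% |

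**Finite samples.** Estimating the slope multiplies the ANCOVA variance by 1 + 1/(N − 4), which is 1 + 1/56 = 1.018 at N = 60. The interval-width ratio is the square root of the variance ratio, times the ratio of t quantiles on 57 and 58 degrees of freedom.

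| N = 60 | ρ = 0.3 | ρ = 0.5 | ρ = 0.7 |
|---|---|---|---|
| Variance, ANCOVA/post | 0.926 | 0.763 | 0.519 |
| Variance, ANCOVA/change | 0.662 | 0.763 | 0.865 |
| 95% CI width, ANCOVA/post | 0.963 | 0.874 | 0.721 |
| 95% CI width, ANCOVA/change | 0.81 | 0.87 | 0.93 |

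A simulation of 40,000 trials per ρ agreed: variance ratios were 0.930, 0.768, 0.525 against post score and 0.665, 0.768, 0.864 against change score. The type I error of each single test was 0.048 to 0.053.

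**When ANCOVA loses.** Against the post score, (1 − ρ²)(1 + 1/(N − 4)) = 1 gives ρ = √(1/(N − 3)), that is 0.164, 0.132 and 0.102 for N = 40, 60 and 100. The worst loss, at ρ = 0, is 1/(N − 4) = 2.8%, 1.8% and 1.0% more variance. Against the change score, ρ = 2/(1 + 1/(N − 4)) − 1 = 0.946, 0.965 and 0.979.

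**Non-random allocation.** Let d be a pre-test difference between groups. The table gives the bias of each estimate.

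| Without counseling, d would | Post score | ANCOVA | Change score |
|---|---|---|---|
| persist in full | d | (1 − ρ)d = 0.7d, 0.5d, 0.3d | 0 |
| shrink to ρd | ρd = 0.3d, 0.5d, 0.7d | 0 | −(1 − ρ)d = −0.7d, −0.5d, −0.3d |

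No method is unbiased in both cases.

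**The case against.** The strongest reply is that this is a preference about efficiency. Under randomisation the t-test is valid, and with no sample size or power target in the documents, no shortfall against a stated goal can be shown. That is correct. It limits how serious the point is, but does not remove a gain available at almost no cost.

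Second, the repeated measures ANOVA may have been meant as group by time, and the one-way sentence may describe a different analysis. This ambiguity is real. Even so, a group-by-time analysis is not baseline-adjusted in the ANCOVA sense.

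Third, a group-by-time analysis could use all three times. With equal correlations, the mean of interim and post-test minus pre-test has relative variance 1.5(1 − ρ) = 1.05, 0.75, 0.45. Post-test ANCOVA at N = 60 has 0.926, 0.763, 0.519, so it is worse at ρ = 0.7. But the two have different targets: the average follow-up effect and the post-test effect. For the same target, ANCOVA of the follow-up mean has relative variance [(1 + ρ)/2 − ρ²] × 1.018 = 0.57, 0.51, 0.37, against 1.05, 0.75, 0.45. Adjustment still wins. What stands is that the plan should say which follow-up target it wants.

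Finally, the SAP is in the past tense, so an adjusted result may be only supplementary. That also stands, and so does the limit that only the available text could be checked.

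**Conclusion.** The point holds: no baseline-adjusted comparison of the groups is stated for outcomes whose pre-test value is collected. It should be fixed, but it is not an invalid test.

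Under random allocation, taking the less favourable of the post-score and change-score readings at each correlation, the large-sample variance saving is 9%, 25% and 15% at ρ = 0.3, 0.5 and 0.7. These sizes rest on assumed correlations, equal SDs and, for the interval widths, an assumed 30 women per group. The direction is secure for ρ between about 0.16 and 0.95 at 20 to 50 women per group; outside that range any loss is very small.

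Under non-random allocation the issue is which assumption the estimate rests on. The bias multiples show how far the methods can diverge; they do not measure a bias found in this trial. Confidence is medium, because correlation, sample size and allocation are all unknown from the text.

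**What to change.** State how women were allocated and which score the t-test uses. Write out the factors in the repeated measures model.

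- **If allocation was random:** estimate the group difference in post-test score by ANCOVA with the same scale's pre-test score as covariate, and treat the interim score likewise as secondary. Report adjusted differences with 95% confidence intervals. Keep the t-test as a sensitivity analysis.
- **If allocation was not random:** report both the ANCOVA and the change-score (group-by-time) estimates, state the assumption behind each, and say that residual confounding remains.
- **If the data have already been analysed:** in either case, add the adjusted analysis as a labelled post hoc supplement and do not replace the stated t-test.

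Birth outcomes have no pre-test value and stay as direct group comparisons.

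The cost is one covariate in the SAS model, a few sentences in the SAP, one degree of freedom, and a rule for women without a pre-test score. No new data are needed.

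### No covariate is planned; if timing of birth, birth weight or preterm birth is analysed, adjusting for gestational age at enrolment is a cheap improvement

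*Combined protocol and SAP*

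**What the plan says.** The title is "The Effect of Nursing Counseling Perceived Stress, Coping and Birth Outcomes Among Pregnant Women", so birth is one of three outcome areas beside stress and coping. The Study Protocol section describes the population: "Pregnant women at risk of preterm birth were enrolled in the study".

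The Statistical Analysis Plan states the group comparison as "A t-test was performed to examine the significance of the differences between the two groups in terms of the dependent variables held". It later adds: "In pairwise comparisons between variables with two categories, t-test between independent groups was applied". The comparison over pre-test, interim follow-up and post-test "was carried out using repeated measures analysis of variance", with paired t-tests between visits. The remaining categorical method is limited in scope: "Chi-Square analysis was used to reveal the relationship between the variables answered as open-ended questions". On the error level: "The value of 0.05 was accepted as the significance level throughout the study".

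The supplied text names no covariate, stratification factor, adjusted model or time-to-event method. It does not define any birth outcome, give an entry window for gestation, or describe how women were allocated. Parts of the document were withheld from review, so I do not count those last three as omissions from the plan.

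**The concern.** Stress and coping are measured before, during and after counselling, so they have a baseline. A birth outcome occurs once. The paired tests and repeated-measures analysis therefore supply no baseline for it, and the stated group comparison that remains is the unadjusted t-test.

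Gestation at enrolment could fill that gap. It is fixed before counselling starts, and it is a floor for gestation at delivery. A woman who enters at 34 weeks cannot deliver at 30; one who enters at 24 weeks can. Where entry gestation varies and some women deliver early, part of the spread in delivery gestation is explained by when they entered. The same should carry over to preterm status and birth weight.

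Two things are at stake. An unadjusted test leaves the explained spread in the error term, which costs power. And if one arm happened to enrol later in pregnancy, its birth results would look better for a reason unrelated to counselling.

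**Working it through.** **Inputs.** The only numerical input in the documents is the 0.05 level; I take it as two-sided. No sample size, power, effect size, standard deviation or event rate is given, so there is no figure of the plan's to reproduce. Everything below is an illustration under stated assumptions.

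**Step 1: gain for a given correlation.** Let r be the correlation between gestation at entry and at delivery. Adjustment multiplies the residual variance by 1 − r². With an assumed standardised difference of 0.5, the number per arm is n = 2(1.96 + 0.84)²(1 − r²)/0.5², which is 63 at r = 0. Power with 63 per arm is Φ(0.5·√(63/2)/√(1 − r²) − 1.96).

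| r | variance cut (r²) | n per arm for 80% power | power at 63 per arm |
|---|---|---|---|
| 0 | 0% | 63 | 80.1% |
| 0.1 | 1% | 63 | 80.5% |
| 0.2 | 4% | 61 | 81.7% |
| 0.3 | 9% | 58 | 83.7% |
| 0.4 | 16% | 53 | 86.5% |
| 0.5 | 25% | 48 | 90.0% |
| 0.6 | 36% | 41 | 93.9% |

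**Step 2: what r is plausible?** Two assumed mechanisms give different answers.

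*Lower bound only.* Entry gestation is uniform over a window. Delivery gestation is normal, capped at 42 weeks, and kept only if later than entry.

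| entry window (weeks) | delivery mean 37, SD 2.5 | mean 36, SD 3 | mean 34, SD 4 |
|---|---|---|---|
| 24–28 | 0.00 | 0.00 | 0.04 |
| 24–34 | 0.04 | 0.10 | 0.24 |
| 24–37 | 0.15 | 0.23 | 0.36 |
| 20–37 | 0.12 | 0.18 | 0.30 |

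So r runs from about 0 to 0.36, and the variance cut from 0% to 0.36² = 13%.

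*Acute risk.* Delivery is entry plus a Weibull waiting time averaging 4 to 8 weeks, capped at 41 weeks, with entry over 24–32, 24–34 or 28–34 weeks. This gives r of roughly 0.34 to 0.70. The 25% and 36% cuts (r = 0.5 and 0.6) belong to this model, which ties delivery to entry by construction.

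**Step 3: effect of an imbalance in entry gestation.** Take the strongest lower-bound case: entry 24–37 weeks, delivery mean 34, SD 4, 60 per arm. The SD of entry gestation is 3.40 weeks, so a 1-SD difference between arm means is 3.40 × √(2/60) = 0.62 weeks. The slope of delivery on entry is 0.357, so the estimate moves by 0.357 × 0.62 = 0.22 weeks, against a standard error of 0.62 weeks. Over all twelve cases the shift is 0.00 to 0.22 weeks, against standard errors of 0.42 to 0.67. At 30 per arm it reaches 0.31 weeks.

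**Step 4: error rate in that same case.** Simulated under random allocation, the unadjusted t-test rejects a true null 5.1% of the time overall. Given an imbalance of k SDs, the test statistic is approximately normal with mean k·r and variance 1 − r². The rejection rate is then the sum of the two tails beyond (1.96 − k·r)/√(1 − r²) and (1.96 + k·r)/√(1 − r²). With r = 0.355 and √(1 − r²) = 0.935:

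- k = 0: cut-offs 2.10 and 2.10, giving 3.6%
- k = 1: cut-offs 1.72 and 2.48, giving 5.0%
- k = 2 (1.24 weeks): cut-offs 1.34 and 2.86, giving 9.3%

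A simulation of 20,000 trials gave 3.7%, 5.9% and 10.4%. A run ten times larger gave 3.7%, 4.9% and 9.8%, so the 5.9% is largely simulation noise. The rate clearly exceeds 5% only for an unusually large imbalance.

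**The case against.** The strongest case against the point has four parts.

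- *The premise is inferred.* Gestation at delivery, birth weight and preterm birth are never named; birth appears as an outcome only in the title. The t-test sentence follows one about scale data and may mainly concern stress and coping scores. A reader might infer that the plan assigns a t-test or chi-square to birth outcomes. The documents do not support that: the t-test is assigned to the dependent variables in general, and chi-square to open-ended answers. This stands, and it is why the point is conditional.
- *The size is unknown.* With narrow, early entry and births mostly near term, r is close to 0 and nothing is gained. A reader might take the 25% to 36% figures as the expected gain here. They rest on an assumed wait of a few weeks from enrolment to delivery, for which the text gives no basis. This stands too.
- *An unadjusted test is not wrong.* A reader might infer an inflated false-positive rate. If allocation was random, the overall rate stays at 5%, and only results conditional on a large imbalance are affected. This stands. It cuts the other way if allocation was not random, because differences in entry gestation could then be systematic.
- *The fix has limits.* The r² formula applies to a linear model for a continuous outcome. No gain has been worked out for preterm birth or birth weight. The plan is also written in the past tense, so a change now may be post hoc.

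None of this argues against naming the covariate. Even at r near 0, adjustment costs almost nothing.

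**Conclusion.** The point holds as a cheap, conditional improvement. The plan's stated group comparison is unadjusted and names no covariate. For outcomes that occur once, in women whose delivery date is bounded below by their enrolment date, an analysis adjusted for entry gestation is the better choice.

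For gestation at delivery, the lower bound alone is worth a 0% to 13% cut in residual variance. In the illustration, a reduction at the top of that range raises 80% power to about 85%. Gains of 25% to 36% need acute risk with delivery soon after enrolment. Protection against imbalance is similarly modest: at most a 0.22-week shift per SD of imbalance at 60 per arm in the lower-bound cases.

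These sizes rest on assumed entry windows, delivery distributions and arm sizes, and on random allocation, none of which the supplied text states. If allocation was not random, the benefit goes beyond precision and adjustment matters more.

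**What to change.** Add to the Statistical Analysis Plan, for whichever of these outcomes is analysed:

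- **Gestational age at delivery and birth weight:** replace the t-test with a linear model containing group and gestational age at enrolment. Report the adjusted difference with its 95% confidence interval.
- **Preterm birth (yes/no):** use a model with group and the same covariate. Report the adjusted risk difference or risk ratio with its 95% confidence interval.
- **Unadjusted tests:** keep them as supportive.
- **Context:** state which birth outcomes are analysed, the entry window for gestation and the method of allocation, if these are not already given elsewhere in the plan.

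The cost is a few sentences and one degree of freedom. Two checks are needed. Confirm that gestation at enrolment is in the dataset; that is likely for this population, but it is an assumption. Confirm also that the change is specified before the group comparison is seen. If the results are already known, label the adjusted analysis post hoc and show it beside the planned test.

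### The planned tests of the scale scores, in classical form, use only women with every score needed; one likelihood-based mixed model testing group-by-time would be a cheap improvement of unknown but possibly small benefit

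*Combined protocol and SAP*

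**What the plan says.** The Statistical Analysis Plan names three kinds of test for the scale scores.

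- **Three time points.** The comparison of pre-test, interim and post-test scores, "as based on the dimension of time, was carried out using repeated measures analysis of variance". A later sentence calls the method one-way: "One-way Repeated Measurement Variance Analysis was used in the analysis of more than one variable taken from the same pregnant women".
- **Pairs of time points.** "To compare the measurements taken from the same pregnant women at different follow-ups, interdependent groups or paired observation t-test was used".
- **Between groups.** "A t-test was performed to examine the significance of the differences between the two groups in terms of the dependent variables held".

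The software is given, but no procedure: "Data analyses were performed via the SAS (Statistical Analysis System Institute, Cary, North Caroline) 9.4 Program".

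Two sentences in the Study Protocol part bear on whether scores could be missing: "Pregnant women at risk of preterm birth were enrolled in the study", and "It was emphasized that they were free to withdraw from the research at any time of their choosing".

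The supplied text does not mention missing scores, an analysis set, imputation, a mixed model, or delivery before a planned measurement. It gives no sample size, no loss rate and no timing of the interim and post-test relative to birth.

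**The concern.** A classical repeated measures ANOVA drops a woman who lacks any one of the three scores. A paired t-test drops her from each pair she cannot complete, and the between-group t-test at a time point drops her if that score is absent. The tests can therefore rest on different sets of women, and scores already collected go unused.

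What is at stake depends on why scores are missing.

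- **Loss unrelated to the score:** only precision suffers.
- **Loss related to the score but alike in both groups:** the between-group comparison at post-test stays essentially unbiased, while change over time among completers within a group can be distorted.
- **Loss related to the score and unequal between groups:** the between-group t-test is biased. It is biased against counseling if the control group loses more high-stress women, and in its favour if the counseling group does.

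**Working it through.** The documents give no figure to reproduce. Everything below is an illustration under stated assumptions.

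**Inputs.** From the SAP: three time points, two groups, significance level 0.05. Assumed: 50 women per group, scores with SD 1, equal correlation r = 0.5 or 0.7 between time points, no true effect. Loss follows logit P(lost) = a + b × score, with b = 0.5 (weak) or 1-1.5 (strong) per SD (odds ratios 1.65, 2.72 and 4.48) and a set to give the stated loss rate.

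**1. Share of women kept.** If a fraction d1 is lost by the interim and a further d2 of the rest by the post-test, the ANOVA keeps (1 − d1)(1 − d2). With 5% and 5% this is 0.95 × 0.95 = 0.90. With 20% and 30% it is 0.80 × 0.70 = 0.56. The pre-to-interim paired t-test keeps 1 − d1, that is 0.95 and 0.80.

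**2. Between-group t-test at post-test.** Loss is driven by the interim score. Bias is the experimental minus control completers' mean; the truth is 0.

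| Loss, control/experimental | Slope | Bias (SD) | Type I error |
|---|---|---|---|
| 30%/30% | all | at most 0.005 | 4.8-5.4% |
| 10%/5% | all | 0.012-0.042 | 4.9-5.7% |
| 30%/15% | weak | 0.033-0.045 | 5.1-5.3% |
| 30%/15% | strong | 0.062-0.107 | 5.5-7.7% |

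If loss is instead driven by the pre-test score, the biases are 0.010-0.042, 0.035-0.051 and 0.058-0.109 SD in the three unequal rows.

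A hand check is possible. In a simulation of 400,000 women (r = 0.5, slope 1), the completers' post-test mean was −0.044, −0.085 and −0.124 SD at 10%, 20% and 30% loss. So 30% against 20% gives 0.124 − 0.085 = 0.039, and 30% against 10% gives 0.124 − 0.044 = 0.080. The 30%/15% case lies between these, in line with the low end of the strong row.

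**3. Loss unrelated to score.** The standard error of the post-test mean, complete-case relative to mixed model, is

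(1/√(1 − m)) / √((1 − R²)/(1 − m) + R²),

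where m is the loss. R² = r² if only the pre-test is available, and 2r²/(1 + r) if the interim is too.

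- Smallest case: m = 0.1, r = 0.5, pre-test only, R² = 0.25. This gives 1.054/√(0.75/0.9 + 0.25) = 1.054/1.041 = 1.013.
- Largest case: m = 0.3, r = 0.7, both scores, R² = 0.98/1.7 = 0.576. This gives 1.195/√(0.424/0.7 + 0.576) = 1.195/1.087 = 1.100.

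The avoidable cost is thus 1-10%.

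**4. Within-group one-way ANOVA.** Loss before the post-test is driven by the interim score. The false-positive rate is about 5% if loss is unrelated to score, 5-7% at 10% loss, about 6-8% at 30% weak loss, and from 8% to about 18% over separate runs at 30% strong loss. The mechanism shows in the large simulation at 30% loss: the completers' interim mean is −0.251 and their post-test mean −0.124, a spurious rise of 0.127 SD where nothing changed.

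**5. Testing group-by-time instead.** In the same kind of scenarios the complete-case group-by-time F-test has type I error of 4.5-6.2%. Its pre-to-post contrast is essentially unbiased under interim-driven loss. Under unequal pre-test-driven loss at 30%/15%, the contrast is still biased by up to about 0.08 SD. The likelihood contrast, computed by monotone regression, has bias of −0.004 to +0.003 SD and type I error of 4.2-5.1% under both unequal mechanisms.

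**6. Limit of the remedy.** If loss depends on the unseen post-test score, t-test bias is 0.022-0.061 SD (10%/5%) and 0.067-0.154 SD (30%/15%). The likelihood contrast still keeps 0.010-0.046 and 0.028-0.120 SD.

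**The case against.** The strongest objection is that the trigger is conjecture. Being at risk of preterm birth does not show that a questionnaire was missed, and freedom to withdraw is standard consent wording. A reader might infer that women who delivered early dropped out of the analysis; the text gives neither measurement timing nor losses, so it does not support that. This objection stands, and it is why the size of the harm cannot be stated.

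A second objection concerns the ANOVA error rate. A reader might infer that the test of counseling carries a false-positive rate of 8-18%. It does not: that figure belongs to a one-way test of change within one group. The main ANOVA sentence is also compatible with a group-by-time analysis, since the one-way label appears only later. Most of the repair comes from testing group-by-time, not from how missing scores are handled. This also stands.

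Third, the SAS procedure is unnamed, so a likelihood fit may have been used. It is not excluded, but none is described.

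Fourth, the type I result for the remedy came from monotone regression, not from the REML and Kenward-Roger fit recommended below. This is a fair limit on that figure.

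What survives is that, under unequal loss driven by an observed score, the t-test and the complete-case contrast can be biased where the likelihood contrast is not.

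**Conclusion.** The point holds as a cheap improvement, at the level of something to consider. As described, the planned tests use only complete sets of the scores they need, and a better-suited method is available in the software already named.

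The bias in the between-group t-test is 0.01-0.04 SD at 10%/5% loss and 0.03-0.11 SD at 30%/15%, and near zero with equal loss. With loss unrelated to score, the avoidable cost is 1-10% in standard error. Every loss rate, imbalance, slope, correlation and group size behind these figures is assumed. The larger values need heavy loss that is twice as common in one group and depends strongly on the score. Nothing in the documents shows that this occurred, or that the conclusion about counseling is wrong. The absence of a missing-score rule is claimed only for the supplied text.

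**What to change.** Analyse each scale score with one likelihood-based mixed model in SAS 9.4: PROC MIXED, REML, unstructured covariance, Kenward-Roger degrees of freedom, with group, time and group-by-time. Keep all three scores as outcomes so that every woman with any score contributes in her own group. Make the group-by-time contrast the test of counseling. If the planned tests have already been run, report this model beside them.

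Supporting steps:

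- Tabulate missing scores by group, time point and reason (delivered, withdrew).
- State whether women who deliver before a planned measurement are still measured, and whether a score after delivery belongs to the question.
- Only if loss is material, add a delta-adjusted sensitivity analysis over a stated range, in each group alone and in both, and report where the conclusion changes.

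The cost is a little more analysis work and no new data. Some bias remains if loss depends on the unseen score, and the model reads correctly only once the status of scores after delivery is settled. With complete data the group-by-time answer is essentially unchanged.

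### Does leaving the birth outcomes unlisted, with 0.05 as the significance level throughout, call for a change to the plan?

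*Combined protocol and SAP*

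**What the plan says.** The title is "The Effect of Nursing Counseling Perceived Stress, Coping and Birth Outcomes Among Pregnant Women", and it is the only place in the available text where birth outcomes appear as outcomes. The other use of the word is in the Study Protocol section, "Pregnant women at risk of preterm birth were enrolled in the study", which describes who was recruited.

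The Statistical Analysis Plan does not name its outcomes one by one. For the between-group comparison it says "A t-test was performed to examine the significance of the differences between the two groups in terms of the dependent variables held". The two sentences before that concern scale data summarised by mean and standard deviation in each arm. For variable types it gives a general rule: mean and standard deviation for measured variables, while "number and percentage were used for the variables determined by counting". For categorical analysis it says "Chi-Square analysis was used to reveal the relationship between the variables answered as open-ended questions".

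The level is set once: "The value of 0.05 was accepted as the significance level throughout the study". No testing order, ranking of outcomes or multiplicity adjustment is described. Analyses are reported in the past tense. Some pages of the document were not available for this review.

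**The concern.** A titled outcome area with no list, no main outcome and a flat 0.05 leaves open how many birth outcomes are tested. If that number is settled after the data are seen, any single significant result could be presented as an effect of counselling on birth outcomes. The chance of such a result with no true effect would then exceed 5% and grow with the number tested.

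A second worry is that the plan mentions no confidence intervals. A non-significant birth outcome would then be reported without showing how large an effect remains compatible with the data. Both points would bear on how far a reader could trust claims in one of the study's three titled areas.

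**Working it through.** **Inputs.** From the document: a significance level of 0.05 (Statistical Analysis Plan, last sentence) and the plural in the title, which suggests at least two birth outcomes. It does not establish that two significance tests were made. Assumed, because the available text gives none of them: the number of tests k, the correlation between outcomes, two-sided tests, the arm sizes, the event rates and a baseline power of 80%.

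**Step 1: the plan's own figure.** For one test, 1 − (1 − 0.05)^1 = 0.05. The stated level is reproduced as a per-test level, and the plan claims nothing more for it.

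**Step 2: several tests, all nulls true.** For k independent tests, the chance of at least one significant result is 1 − 0.95^k. For correlated outcomes it comes from numerical integration over equicorrelated normal statistics.

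| k | correlation 0 | correlation 0.5 | correlation 0.8 |
|---|---|---|---|
| 2 | 0.0975 | 0.0907 | 0.0781 |
| 3 | 0.1426 | 0.1254 | 0.0982 |
| 5 | 0.2262 | 0.1828 | 0.1273 |
| 8 | 0.3366 | 0.2501 | 0.1575 |

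Only the k = 2 row has any footing in the document. All rows apply only if no main birth outcome was fixed in advance in text not seen here.

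**Step 3: what adjustment would cost.** An effect with 80% power at 0.05 has a standardised size of 1.960 + 0.842 = 2.802.
- Bonferroni over three outcomes: critical value 2.394, so power is Φ(2.802 − 2.394) = Φ(0.408) = 0.66.
- Bonferroni over five outcomes: critical value 2.576, so power is Φ(2.802 − 2.576) = Φ(0.226) = 0.59.

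Holm loses no more than this. Control of the group-wide error is therefore bought with up to 14 or 21 percentage points of power per outcome (80 − 66; 80 − 59).

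**Step 4: would naming a main outcome settle it?** Suppose one birth outcome is tested at 0.05 and two others are tested by Holm, without waiting for the first to succeed. With independent nulls, Holm on the pair has error 1 − 0.975² = 0.0494. The total is 1 − 0.95 × 0.975² = 1 − 0.95 × 0.9506 = 0.097, about the same as two unadjusted tests. Five per cent is held only if the others are tested after the main one succeeds, or carry no significance claim, and only if the main one was chosen before results were seen.

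**Step 5: intervals.** Both can be formed from what the plan already reports, plus arm sizes.
- Risk difference, approximate half-width 1.96 × √(2p(1 − p)/n). At an assumed 30% event rate and 50 per arm: 1.96 × √(2 × 0.3 × 0.7/50) = 0.180, or 18 points.
- Mean difference, half-width t × √(2/n) in SD units. At 50 per arm: 1.984 × √(2/50) = 0.397 SD.

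The inputs are numbers and percentages for counted variables, and means and standard deviations for measured ones. The plan provides for both.

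**The case for a change.** The strongest case for a change is that the 0.05 rule is an affirmative statement, not a silence. Even a list of birth outcomes elsewhere in the document would leave each one tested at the full level. A short outcome table needs no new data, and one main outcome chosen in advance would hold 5% with no loss of power for that outcome.

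Part of this stands. The available text leaves the number of birth-outcome tests open. If several were tested with none singled out beforehand, the inflation in the table is real.

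The rest does not carry the point to a change in the plan:
- A per-test level is an accepted convention, and the plan does not claim to control error over any set of outcomes.
- The available text does not show that every birth outcome was tested. Its between-group t-test sentence follows directly on scale data, and counted birth outcomes could be reported by number and percentage alone.
- The benefit of a named main outcome depends on naming it before results. With the analyses described as complete, that moment may have passed.
- Birth outcomes are not a natural family on their own. The stress and coping scales, their sub-dimensions and the repeated time points raise the same question, so adjusting one area would leave study-wide error where it is.

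**Conclusion.** The observation is accurate for the available text, but it describes missing detail rather than a wrong analysis. Analysts and authors fill this gap sensibly when they report: they state how many birth outcomes were examined, show all of them, and treat as exploratory any not fixed beforehand. A reader can then judge an isolated p-value below 0.05.

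The supported size is modest and conditional: 7.8% to 9.8% for two outcomes, if two were tested at 0.05, neither was fixed as the main one, and correlation lies between 0.8 and 0. The larger percentages, up to 33.7% for eight independent outcomes, depend on counts that the document does not give.

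Adjusting across unranked outcomes trades that error for power and is a matter of judgement. Confidence intervals would improve the report, but they are an addition that can be computed from the planned summaries and arm sizes. No change to the plan is called for.
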